Table CGAL.5.1. Example of Missing Data Imputation Outcome	14
Table CGAL.5.2. Patient Population with Baseline and Postbaseline Definitions by Study Phase and Type of Analysis	21
Table CGAL.5.3. Other Secondary and Exploratory Efficacy Variables and Their Derivation.....	30
Table CGAL.5.4. Criteria for Treatment-Emergent, Potentially Clinical Significant and Categorical Changes and Sustained Elevation in Vital Signs and Weight	38
Table CGAL.5.5. Criteria for Treatment-Emergent Changes in ECG Intervals and Heart Rate.....	40
Table CGAL.5.6. Sample ADA Assay Results.....	43
Table CGAL.5.7. Sample Clinical ADA Interpretation Results.....	43
Table CGAL.5.8. Definition of Subgroup Variables	45
Table CGAL.5.9. Subgroup Analyses	46

Table of Contents

Appendix		Page
Appendix 1.	Description of Important Protocol Deviations	53

3. Revision History

Statistical Analysis Plan (SAP) Version 1 was approved on 18 December 2014.

Statistical Analysis Plan Version 2 was approved prior to first patient visit and any unblinding. The overall changes and rationale for the changes incorporated in Version 2 are as follows:

- The electronic patient reported outcome (ePRO) diary will now collect the average duration and average pain for the time period rather than for each attack. Thus the derivation for mean severity and mean duration of cluster headache attack were updated.
- The approach for missing data was updated for each weekly interval.
 - 1) If there are less than or equal to 3 days with nonmissing answer to cluster headache attack frequency in the weekly interval; or 2) the primary efficacy compliance rate is less than or equal to 50%, then the weekly interval will be considered missing;
 - Otherwise, 1) if there are greater than or equal to 4 days with nonmissing answer to cluster headache attack frequency in the weekly interval; and 2) the primary efficacy compliance rate is greater than 50%, then the average number of cluster headache attacks across the nonmissing days will be used to impute the missing days.
- The algorithm for pooling of sites was updated.
- The primary endpoint point estimate was updated to use the unadjusted estimate, and the median unbiased estimate will be used for sensitivity.
- ePRO diary compliance was updated to calculate both ePRO diary primary efficacy compliance rate and overall ePRO diary compliance rate.
- Addition of analysis for change from baseline in total weekly dose of sumatriptan Sc, sumatriptan nasal spray, and zolmitriptan nasal spray separately as well as combined.

Statistical Analysis Plan Version 3 was approved prior to IA1. The changes incorporated in Version 3 are as follows:

- Posttreatment follow-up phase safety analyses will have only 1 baseline.
- A section on protocol violations to be identified was added.
- Sensitivity analyses were updated, to be consistent with other Phase 3 studies of LY2951742.
- Infections section will only deal with upper respiratory tract infections; analyses were modified to be consistent with other Phase 3 studies of LY2951742.
- For Columbia-Suicide Severity Rating Scale (C-SSRS), 1 bullet was split into 2 to enhance readability, and baseline definition for improvement from baseline analysis was clarified.

- Criteria for sustained elevation in diastolic blood pressure was changed to be consistent with the single time point analysis.
- An additional criteria threshold for QTc increase was added.
- Analyses of elevations in hepatic laboratory tests were clarified, and an additional subset was added.
- Immunogenicity analyses were updated to be consistent with other Phase 3 studies of LY2951742.
- An additional subgroup analysis category, for age, was added.
- Some minor corrections and clarifications were made.

Statistical Analysis Plan Version 4 was approved after the last patient was randomized and prior to interim analysis (the first and final assessment of primary efficacy endpoint after all patients completed double-blind phase, which is the first unblinding to study team). Enrollment in the trial was terminated (due to enrollment infeasibility) prior to reaching the sample size target for the originally planned interim analysis. Therefore, the planned interim analysis for sample size re-estimation did not occur.

In the SAP Version 4, the updates were made mainly for incorporating the recent learnings from migraine data or for consistency across the galcanezumab program. The changes incorporated in Version 4 of the SAP are summarized as follows:

- LY2951742 was replaced by galcanezumab in the body of the SAP.
- Consistent with the primary endpoint and analysis methodology for the pivotal migraine studies, the primary endpoint was updated to be the overall treatment effect over the Weeks 1 to 3 during the double-blind treatment phase, rather than the treatment effect at the single time point, Week 3.
- In Section 5.4.1.2, the exploratory endpoints for severity and duration of cluster headache attack pain and for the abortive medications were updated to clarify the research questions and the derivations were modified correspondingly.
- In Section 5.5.1.1 and 5.5.8.3, it was clarified that, for other secondary and exploratory efficacy measures that are not derived from cluster headache frequency, the baseline average daily cluster headache attack frequency category variable is included in the statistical analysis models.
- The list of analyses for other secondary and exploratory efficacy variables were updated in Table CGAL.5.3. Last observation carried forward (LOCF) analysis for some exploratory variables was removed.
- Since no partially completed diary can be submitted, the ePRO diary primary efficacy compliance and overall ePRO diary compliance are combined into 1 diary compliance calculation in Section 5.5.6.

- In Section 5.5.1 and Table CGAL.5.2, safety population and modal treatment description for SP III were added for safety analyses since it is more appropriate to present safety results by the actual treatments patients received.
- Terminologies and identification criteria were updated for adverse event of special interest (AESIs) for the consistency across the galcanezumab program.
- In Section 5.5.9.1.3, detailed baseline and postbaseline definition for vital signs and weight were added. The patient populations for analysis that do not satisfy treatment-emergent definition were removed from Table CGAL.5.4.
- In Section 5.5.9.1.4, the parameter of large clinical trial population based QT correction (QTcLCTPB) was removed for electrocardiogram (ECG) analysis. The detailed baseline and postbaseline definitions for ECG were added.
- In Section 5.5.9.2, for continuous safety measures, Box-whisker plots with summary tables for SP III replaced LOCF and repeated measures analysis.
- Section 5.5.9.1.6 of Immunogenicity was updated to clarify definitions and modify analyses to focus on evaluation of the incidence of baseline anti-drug antibodies (ADA) and treatment-emergent ADA.
- Subgroup analysis for safety endpoints were removed due to the small size of the study. A few subgroup variables for the efficacy endpoint were removed due to the small size in subgroups.
- Section 5.6, Interim Analysis is updated to explain the changes in the interim analysis plan.
- Since the originally planned interim analysis for sample size re-estimation will not be conducted due to enrollment infeasibility, all languages and methodology descriptions related to sample size increase are removed.
- In Section 5.8, reports to be generated were updated to reflect that analyses from all SPs specified in this SAP will be performed at the interim analysis instead of only performing analyses for SP III. However, the analyses conducted for SP III will be deemed final since all patients will complete SP III at the interim analysis. The analyses using data from SP IV will be rerun and updated when the completed data are available at the final database lock.
- An appendix of important protocol deviations was added.
- Other minor corrections, modifications, and clarifications were made.

Statistical Analysis Plan Version 5 has been approved prior to the interim analysis (the first and final assessment of primary efficacy endpoint after all patients completed double-blind phase, which is the first unblinding to study team). There is no modification to the primary analysis methodologies for the primary, key secondary, and other secondary efficacy endpoints. The changes incorporated in Version 5 are summarized as follows:

- In Section [5.4.1.2](#), the exploratory endpoint for cluster headache attack duration was modified from “average weekly cluster headache attack minutes per attack for the remaining cluster headache days” to “weekly total cluster headache attack duration.” An exploratory responder endpoint for the weekly total cluster headache attack duration that is defined as 30% or greater reduction is also added.
- In Section [5.5.9.1.2](#), removed the requirement of needing at least 4 events occurred in at least one treatment to display p-value.
- In [Table CGAL.5.4](#), added additional patient populations for analysis of treatment-emergent, potentially clinically significant changes and sustained elevation in vital signs.
- In Section [5.5.10](#), additional subgroup variables were added for subgroup analysis.

CCI

- In the table of Description of Important Protocol Deviations in [Appendix 1](#), updated the data source of the Important Protocol Deviations (IPDs) to only display the final data source for the IPD analysis. Two new IPDs were added.

4. Study Objectives

4.1. Primary Objective

The primary objective is to assess the efficacy of galcanezumab 300 mg every 30 days compared with placebo in reducing the frequency of weekly cluster headache attacks in patients with episodic cluster headache. The primary outcome measure will be the weekly cluster headache attack frequency. The primary endpoint will be the overall mean change from baseline in weekly cluster headache attack frequency across Weeks 1 to 3 with galcanezumab compared with placebo. Baseline is defined as the last 7 days in the eligibility report (prerandomization diary phase).

4.2. Secondary Objectives

4.2.1. Gated Objective

To assess the efficacy of galcanezumab compared with placebo in the proportion of patients meeting response at Week 3. For this analysis, response is defined as a reduction from baseline of 50% or greater in the weekly cluster headache attack frequency.

4.2.2. Other Secondary Objectives

- To assess whether galcanezumab is superior to placebo on the following:
 - The proportion of patients with a 50% or greater reduction in the weekly number of cluster headache attacks from baseline for each weekly interval through Week 8
 - The proportion of patients with a 30% or greater reduction in the weekly number of cluster headache attacks from baseline for each weekly interval through Week 8
 - Mean change in the weekly cluster headache attack frequency from baseline for each weekly interval through Week 8
 - Proportion of patients reporting a score of 1 (“very much better”) or 2 (“much better”) on the Patient Global Impression of Improvement (PGI-I) at Week 4 and Week 8.
- To compare the safety and tolerability of galcanezumab with placebo in patients with episodic cluster headache using the following measures:
 - spontaneously reported treatment-emergent adverse events (TEAEs)
 - serious adverse events (SAEs)
 - discontinuation rates
 - suicidal ideation and behaviors assessed by solicited questioning using the C-SSRS

- To assess the development and consequences of ADA to galcanezumab in patients exposed to galcanezumab; to provide samples for subsequent evaluation of neutralizing ADA (NAb).
- To evaluate the pharmacokinetics of galcanezumab.

4.3. Exploratory Objectives

To assess whether galcanezumab is superior to placebo as measured by the following:

- Mean change in the weekly number of times an abortive medication was taken from baseline for each weekly interval through Week 8 comparing galcanezumab with placebo.
- Change in percentage of times using oxygen from baseline for each weekly interval through Week 8 comparing galcanezumab with placebo.
- Change in percentage of times using triptan from baseline for each weekly interval through Week 8 comparing galcanezumab with placebo.
- Change in percentage of times of using acetaminophen/paracetamol or nonsteroidal anti-inflammatory drugs (NSAIDs) from baseline for each weekly interval through Week 8 comparing galcanezumab with placebo.
- The proportion of patients with a 75% or greater reduction in the weekly number of cluster headache attacks from baseline for each weekly interval through Week 8 comparing galcanezumab with placebo.
- The proportion of patients with a 100% reduction in the weekly number of cluster headache attacks from baseline for each weekly interval through Week 8 comparing galcanezumab with placebo.
- Mean change from baseline in the cluster headache attack average weekly pain severity (based on 5-point scale) from baseline through Week 8 comparing galcanezumab with placebo.

5. A Priori Statistical Methods

5.1. Study Design

Study CGAL is a Phase 3 multi-center, outpatient, randomized, double-blind, placebo-controlled study of LY2951742 300 mg in the prevention of episodic cluster headache. The study has 4 study phases (SP): SP I (screening/washout), SP II (pre-randomization diary), SP III (randomized, double-blind, placebo-controlled treatment), and SP IV (post-treatment follow-up). Patients who discontinue the study during the double-blind treatment phase should enter the post-treatment follow-up phase.

5.2. Determination of Sample Size

The study is planned to have a minimum of approximately 162 patients randomized 1:1 to placebo or galcanezumab 300 mg with the opportunity to increase the final sample size at an interim analysis if indicated in order to maintain a well-powered study. To preserve blinding, details of the sample size and power calculations are omitted from this SAP and are provided in a separate document to the Ethical Review Board (ERB).

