12.1. Determination of Sample Size

The study is planned to have a minimum of approximately 162 patients randomized 1:1 to placebo or LY2951742 with the opportunity to increase the final sample size at an interim analysis if indicated in order to maintain a well powered study. To preserve blinding, details of the sample size and power calculations are omitted from this protocol and are provided in a separate document to the ERB.

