12.2. Statistical and Analytical Plans

12.2.1. General Considerations

Unless otherwise specified, efficacy analyses during SP III will be conducted on an intent-to-treat (ITT) population, which include all patients who are randomized and receive at least 1 dose of IP. Patients in the ITT population will be analyzed according to the treatment group to which they were randomized. Safety analyses during SP III will be conducted on the safety population, which also includes all patients who were randomized and receive at least 1 dose of study drug. However, patients will be analyzed by actual study treatment received most often (modal treatment) during the double-blind treatment phase. When change from baseline is assessed, the patient will be included in the analysis only if he/she has a baseline and a post-baseline measurement.

For analyses of the post-treatment phase, the post-treatment population will be used. Post-treatment population will be defined as all patients who entered the post-treatment phase (SP IV) as indicated by entering any post-treatment visit.

Details related to handling of missing data will be described in the SAP.

Treatment effects will be evaluated based on a 2-sided significance level of 0.05 for all the efficacy and safety analyses unless otherwise stated. The 95% confidence intervals (CIs) for the difference in least-square means (LSMeans) between treatment groups will be presented. Adjustments for multiple comparisons for the analyses corresponding to the primary and gated secondary objectives are described in the sections on the primary and secondary efficacy analyses below. There will be no adjustments for multiplicity for analyses of other data.

Categorical comparisons between treatment groups will be performed using Fisher's exact tests, where appropriate.

Any change to the data analysis methods described in the protocol will require an amendment ONLY if it changes a principal feature of the protocol. Any other change to the data analysis methods described in the protocol, and the justification for making the changes, will be described in the statistical analysis plan (SAP) and/or in the clinical study report.

Additional exploratory analyses of the data will be conducted as deemed appropriate.

Statistical analysis of this study will be the responsibility of Eli Lilly and Company or its designee. SAS® software will be used to perform most or all statistical analyses.

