Treatment effects will be evaluated based on a 2-sided significance level of 0.05 for all the other efficacy and safety analyses. The 95% confidence intervals for the difference in least-square means (LSMeans) between treatment groups will be presented. Adjustments for multiple comparisons for the analyses corresponding to the primary and gated secondary objectives are described in the sections on the primary and secondary efficacy analyses below. There will be no adjustments for multiplicity for analyses of other data.

A repeated measures analysis refers to a restricted maximum likelihood (REML)-based, mixed-effects repeated measures (MMRM) analysis using all the longitudinal observations at each postbaseline visit/week.

Categorical comparisons between treatment groups for safety measures will be performed using Fisher's exact tests, where appropriate.

Any change to the data analysis methods described in the protocol will require an amendment ONLY if it changes a principal feature of the protocol. Any other change to the data analysis methods described in the protocol, and the justification for making the changes, will be described in the SAP and/or in the clinical study report (CSR).

Additional exploratory analyses of the data will be conducted as deemed appropriate.

Statistical analysis of this study will be the responsibility of Eli Lilly and Company (Lilly) or designee. SAS® software will be used to perform most or all statistical analyses.

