5.6. Interim Analyses

Up to 2 interim analyses were planned for Study CGAL. Interim analysis 1 during SP III may be conducted that may result in increasing the sample size or stopping the trial for futility. Details were documented in the Statistical Analysis Center SAP, ERB supplement, and DMC Charter. However, this interim analysis for sample size re-estimation will not happen due to enrollment infeasibility. The DMC will still independently monitor patient safety during this trial.

The other interim analysis that was planned will be conducted after all patients have had the opportunity to complete 8 weeks of treatment (SP III) and, thus, will be the final analysis of the primary efficacy endpoint. The interim analysis will be conducted using internal unblinded study team members who do not have direct interaction with sites.

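### SAP 5.2, Protocol 12.1 and the synopsis still promise a minimum of about 162 patients and an interim increase; that interim is cancelled and 162 was very likely not reached

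*SAP*

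**What the plan says.** Three current statements describe the sample size.

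- SAP 5.2: a trial "planned to have a minimum of approximately 162 patients randomized 1:1 to placebo or galcanezumab 300 mg with the opportunity to increase", subject to an interim analysis.
- Protocol 12.1: the same minimum of about 162, "with the opportunity to increase the final sample size at an interim analysis if indicated in order to maintain a well powered study".
- Protocol synopsis, statistical methods paragraph: the same sentence as Protocol 12.1.

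Two equally current statements withdraw the interim. SAP 5.6 says that "this interim analysis for sample size re-estimation will not happen due to enrollment infeasibility", and Protocol 12.2.12 carries the same words.

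The SAP revision history (Section 3) adds two facts. On timing: "Statistical Analysis Plan Version 4 was approved after the last patient was randomized". On recruitment: "Enrollment in the trial was terminated (due to enrollment infeasibility) prior to reaching the sample size target for the originally planned interim analysis". Version 5, the current SAP, follows Version 4.

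Both documents state that the power calculation is kept in a separate document for the ethical review board, to protect blinding.

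**The concern.** The sample-size section is where a reader looks for the size of the trial and for what protects its power. Read alone, each of the three places gives a floor of about 162 patients and a mechanism for going above it. The mechanism has been withdrawn elsewhere in the same documents, and the floor probably was not met. None of the three places cross-refers to the section that withdraws it.

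What is at stake is how the result is read, above all a non-significant one. Someone relying on SAP 5.2 would credit the trial with more information, and a stronger guard against low power, than it appears to have had.

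**Working it through.** **Step 1: the option to increase.** SAP 5.2, Protocol 12.1 and the synopsis paragraph make any increase depend on an interim analysis. SAP 5.6 and Protocol 12.2.12 say the re-estimation interim will not take place. The only other interim described is the analysis after Study Phase III, which is the final analysis of the primary endpoint and cannot lead to more patients. The option is void in both documents.

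**Step 2: the figure of 162.** SAP 5.6 and Protocol 12.2.12 do not mention it, so they do not cancel it. Its status has to be inferred:

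- Let T be the sample-size target for the re-estimation interim and N the number randomized. Neither is stated.
- The revision history says enrollment ended before T was reached, so N < T if T counts randomized patients.
- An interim that decides whether to go beyond a minimum would ordinarily be held at or before that minimum, so T ≤ 162 is the natural assumption.
- Together these give N < T ≤ 162.

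The conclusion would fail only if T exceeded 162, or if T counted something other than randomized patients, for example completers. Hence very likely, not documented.

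**Step 3: timing.** The revision history places Version 4 after the last randomization, and Version 5 is later. The total was therefore fixed when SAP 5.2 was last approved. The same cannot be shown for the protocol. Amendment (d) is dated 29 March 2018, the supplied SAP text gives no date for Version 4, and SAP 5.5 lists protocol amendments only up to (c).

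**Step 4: can 162 be reproduced?** No. Effect size, standard deviation, power and dropout allowance are withheld by design. The planned counts in the synopsis table do agree with each other: 146/162 = 0.901, about 10% not completing, and 162/231 = 0.701, about 30% failing screening.

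**Step 5: what a smaller N would mean.** With 1:1 allocation and common standard deviation σ, the standard error of a difference in means is

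SE = σ × sqrt(2/(N/2)) = 2σ/sqrt(N).

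The ratio to 162 patients is sqrt(162/N). At fixed significance level and power, the detectable difference scales the same way. For a difference in response proportions the scaling also holds, approximately, at fixed proportions.

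| N (assumed) | sqrt(162/N) | Increase in CI width |
|---|---|---|
| 162 | 1.000 | none |
| 140 | 1.076 | about 8% |
| 120 | 1.162 | about 16% |
| 100 | 1.273 | about 27% |
| 80 | 1.423 | about 42% |

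The N values below 162 are assumptions chosen to show a range. None comes from the documents.

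**The case against.** The strongest reply is that this is a leftover sentence and that the change is openly disclosed. SAP 5.6, Protocol 12.2.12 and the revision history all report the cancellation, and nobody running the analysis would be misled. The 162 figure already stands in a sentence about what is planned. That is fair as far as it goes, and it limits the seriousness of the point. But a planned minimum is a floor, not a target, and a safeguard that cannot operate should not stand as current in the section that defines the sample size. The synopsis table is different: it labels its figures as planned, claims no floor, and needs no change.

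A reader might infer more than the documents support:

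- **That SAP 5.6 and Protocol 12.2.12 cancel the 162.** They cancel only the re-estimation interim.
- **That the trial is shown to have fallen short, or to be 8% to 42% less precise.** The shortfall is an inference, and the percentages are generic scaling on assumed N, with zero included.
- **That the protocol kept this text after recruitment was known to have closed.** The timing is documented for the SAP only.
- **That the missing power calculation is a defect.** Withholding it is a stated blinding choice, and whether the ethical review board document was updated cannot be known from here.
- **That the Version 4 change list, which says such wording was removed, proves an error.** A change list differing from current text is not an error. The point rests on the current sections alone.

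**Conclusion.** The point holds within limits. The contradiction about the option to increase is certain, because it lies between current sections of both documents. That the minimum of about 162 was not reached is a strong inference, resting on the assumption that the interim's target was a count of randomized patients no larger than 162.

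The size of any loss in power cannot be determined, because neither the number randomized nor the planned power is given. Only the relation sqrt(162/N) can be stated, assuming equal allocation and unchanged variance.

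Type I error is not affected: no re-estimation took place, and the final analysis carries no adaptive adjustment. The planned analyses stand. For least-squares mean differences, which include the primary endpoint, SAP 5.5.1 commits to intervals ("The 95% confidence intervals for the difference in least-square means (LSMeans) between treatment groups will be presented"), so the precision achieved will be visible in the results. The sponsor should correct the text, but the validity of the trial does not depend on it.

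**What to change.** In SAP 5.2, Protocol 12.1 and the statistical paragraph of the synopsis:

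1. Delete the option to increase the sample size.
2. Describe 162 as the original target, not a minimum.
3. Cross-refer to SAP 5.6 and Protocol 12.2.12.

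In SAP 5.2 only, where the total was already fixed at last approval, also state the number randomized with arms pooled, and that enrollment stopped because it was infeasible. A pooled total reveals no treatment assignment.

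The cost is minor rewording in three places and one added number. No patients are added and no analysis changes. The only downside for the sponsor is a less favorable stated size.
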